3.1 Study Design

This is a randomised, double-blind, placebo-controlled, multicentre, multinational, prospective study in patients with operable CTEPH prior to PEA with high preoperative PVR ($>800 \text{ dyn}\cdot\text{s}\cdot\text{cm}^{-5}$). Eligible patients will be randomly assigned to riociguat or matching placebo tid in a 1:1 ratio. A total of 88 patients are planned to randomly assign at 4 sites in North America and Europe.

A schematic of the study design is presented in Figure 3-1.

Figure 3-1

Study Schematic

Abbreviations: PEA, pulmonary endarterectomy; RHC, right heart catheterisation; V, visit

Patients will undergo a screening period of up to 89 days prior to baseline (Visit 1). Following completion of the pretreatment screening phase, eligible study patients will be randomly assigned into the study.

The study will comprise 3 study periods:

- **Screening Period (Day -89 to Day 1):** The screening period of up to 90 days will be used to assess eligibility of patients and to allow for the washout of prohibited medications. Screening visit (V0) and randomisation visit (V1) can occur on the same day.
- **Treatment Period (Day 1 [Baseline] through Day 90):** Patients will be randomly assigned on Day 1 to receive either riociguat or matching placebo tid in a 1:1 ratio for 3 months. The study drug will be initiated at 1 mg and the dosage can be increased by 0.5 mg at 2-week intervals based on tolerability (SBP) up to a maximum dose of 2.5 mg tid based on the algorithm mentioned in Section 5.2. The study drug will be initiated no later than 180 days after right heart catheterisation (RHC) (used for screening of patients) and within 90 days of planned RHC before PEA. At Visit 2, RHC will be performed per site procedures no more than 1 week prior to PEA, which will be conducted by the principal surgeon of the site. The study drug will be discontinued once PEA is performed. The last study dose will be given on the morning of PEA surgery. The patient will remain hospitalised per the investigator's discretion.
- **Follow-up Period:** A follow-up visit is planned at 6 months after PEA, at which time RHC will also be performed per study site procedures.

A telephonic call visit is planned during treatment period and at Day 186±10 during follow-up period, where treating physician or designee will call patient to ask questions related to patient's well-being and any adverse events.

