4.1.2 Exclusion Criteria

Patients meeting any of the following criteria will be excluded from the study:

1. Has unstable disease in need of urgent PEA surgery as determined by the treating physician
2. Has known hypersensitivity, allergic, or adverse reactions to riociguat or any of the excipients comprising riociguat tablets
3. Has known active hepatitis A immunoglobulin M, hepatitis B surface antigen, or hepatitis C antibody
4. Is human immunodeficiency virus positive
5. Has pulmonary veno-occlusive disease
6. Has symptomatic hypotension
7. Has symptomatic carotid disease
8. Has significant coronary atherosclerotic disease in need of intervention
9. Has severe left heart disease in need of intervention
10. Has redo sternotomy
11. Has received any background therapy for PAH in the preceding 30 days before Visit 1 including ERAs, PDE5 inhibitors, or prostanooids
12. Is receiving nitrates, NO donors (eg, amyl nitrite), ERAs, prostanooids, specific PDE5 inhibitors, nonspecific phosphodiesterase inhibitors (eg, dipyridamole, theophylline)
13. Is receiving strong cytochrome P450 and P-glycoprotein/breast cancer resistance protein inhibitors
14. Is receiving strong cytochrome P450 3A inducers
15. Has creatinine clearance <15 mL/min or is on any form of dialysis
16. Has severe hepatic impairment classified as Child-Pugh B or C

17. Has received an investigational drug within the past 4 weeks before Visit 1
18. Is a lactating or pregnant (as demonstrated by a serum or urine dipstick pregnancy test) woman, or not willing to take measures not to become pregnant during the 3-month treatment study period and 1 month after the last dose of study drug administered
19. Has smoked or used tobacco in any form, including snuff or chewing within 3 months prior to Visit 1
20. Has idiopathic interstitial pneumonitis

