5.8 Prior and Concomitant Therapy

Patients must be treated with anticoagulants. Drugs with the potential to reduce blood pressure should be used with caution in combination with riociguat, and no drugs named in the exclusion criteria may be administered to patients on riociguat therapy, including nitrates, NO donors, phosphodiesterase inhibitors (including PDE5 inhibitors), ERAs and prostanooids (see exclusion criteria Section 4.1.2).

All concomitant medications taken by the patient during the study, from the date of signature of the informed consent will be recorded in the appropriate section of the eCRF. The minimum requirement is that drug name and the dates of administration are to be recorded. This will include all prescription drugs, herbal products, vitamins, minerals, and over-the-counter medications. Any changes in concomitant medications will also be recorded in the patient's eCRF.

Any concomitant medication deemed necessary for the welfare of the patient during the study may be given at the discretion of the investigator. However, it is the responsibility of the investigator to ensure that details regarding the medication are recorded in full in the eCRF.

6 Study Assessments and Procedures

Before any study procedures are performed, all potential patients will sign an informed consent form (ICF). Patients will have the opportunity to have any questions answered before signing the ICF. The investigator must address all questions raised by the patient. The investigator will also sign the ICF.

Patients will undergo the procedures at time points specified in the Schedule of Events (Table 12-1).

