7.6 Analysis Sets

The following analysis sets will be used in the statistical analyses.

Intent-to-treat (ITT) set: The ITT set will consist of all participants who received at least one dosage of randomised study drug. All analyses using the ITT will group participants according to randomised treatment.

PEA set: The PEA set will consist of all ITT participants who actually undergo PEA. All analyses using the PEA will group participants according to randomised treatment.

Per-protocol set (PPS): The PPS will consist of all ITT participants who fulfil all inclusion/exclusion criteria, have at least 80% overall dose compliance with study drug, have not taken any prohibited medication, have no significant protocol deviations, have valid PVR assessments at baseline and Visit 2, and undergo PEA as planned. All analyses using the PPS will group participants according to treatment actually received. A blind data review of data will identify which participants will be included in the PPS.

Safety set: The safety set will consist of all participants who received any study drug. All analyses using the safety set will group participants according to treatment actually received.

The ITT set will be used as the primary efficacy analysis set including primary, secondary, and exploratory efficacy analyses.

The PPS will be used in the primary and secondary efficacy analyses as supportive analyses. The exploratory efficacy analyses may use PPS in a way more relevant to the specific question, which is specified in the SAP.

The safety set will be used in safety analyses.

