4.3.3. Per Protocol Set (PPS)

The PPS will consist of all ITT patients who fulfil all inclusion/exclusion criteria, have at least 80% overall dose compliance with study drug, have not taken any prohibited medication, have no significant protocol deviations, have valid PVR assessments at baseline (from patient history) and Visit 2, and undergo PEA as planned. All analyses using the PPS will group patients according to treatment actually received. A blind review of data will identify which patients will be included in the PPS.

The PPS will be used in the primary and secondary efficacy analyses as supportive analyses.

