8.2.2. Composite Clinical Endpoints

Composite clinical endpoints from randomisation to Visit 4 will be tabulated by treatment group containing the number and percentage of patients with an event as well as the number of event for the PEA set and the PPS. The Fisher exact test will be utilised to test the proportion difference along with the Clopper-Pearson exact CI when applicable. For analysis based on the ordinal response of functional class, the row mean score from the Cochran Mantel-Haenszel test will be used to test the response difference between groups.

Composite clinical endpoints include following clinical endpoints:

- All-cause death

All deaths that happen after randomisation until the date of Visit 4, 6 months after the PEA, will be included.

- PH-related hospitalisation

All PH-related hospitalisation except the in-hospital care after PEA from randomisation until 6 months after PEA will be included.

- Need for PAH-targeted therapy

All PAH-targeted therapy from randomisation until 6 months after PEA will be included.

- Functional class unchanged or worse

When comparing the functional class assessment at Visit 1 with the functional class assessment at other visits, the same class will be defined as unchanged, and a higher class will be defined as worse. The worst case after treatment will be used.

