8.3. Exploratory Efficacy Endpoints

Exploratory efficacy endpoints are defined in Section 3.2.3. No formal assessment of difference between treatment groups will be performed for any of the exploratory efficacy endpoints. The difference between treatment groups in exploratory efficacy endpoints will be estimated with 95% CIs to quantify the treatment effect.

Summary tables presenting observed values and changes from baseline for NT-proBNP measurement concentration (pg/mL), cardiac output (L/min), cardiac index (L/min/m²), mRAP (mmHg), mPAP (mmHg), and PAWP (mmHg) will be provided for each treatment group by scheduled visits using descriptive statistics. The difference in the change from baseline between treatment groups with 95% CIs will be estimated non-parametrically using Hodges-Lehmann estimation of location shift in the tables. The analyses will be based on the PEA set and the PPS.

Hospital length of stay in days and ICU length of stay in days will be summarised using descriptive statistics. The difference between treatment groups with 95% CI will be estimated non-parametrically using Hodges-Lehmann estimation of location shift in the table. The analyses will be based on the PEA set.

Time from start of ICU stay to end of mechanical ventilation (in hours) will be analysed using the Kaplan Meier method. Median and quartiles in days and associated 95% CI will be calculated using the LOGLOG transformation. All patients stayed in ICU who do not have end date of mechanical ventilation will be censored at the time of discharged from the ICU. The analyses will be based on the PEA set.

Proportion of in-hospital mortality will be summarised using the frequency counts and percentages for the PEA set. Proportion difference between treatment groups along with the Clopper-Pearson exact CI will be provided

The proportion of patients who need PAH-targeted therapy immediately after PEA to Visit 4 will be summarised using the frequency counts and percentages for the PEA set and the PPS. Proportion difference between treatment groups along with the Clopper-Pearson exact CI will be provided.

WHO functional class will be summarised by scheduled visit for each treatment group. Shift table of baseline functional class versus functional class at each postbaseline scheduled visit will be provided. The analyses will be based on the PEA set and the PPS.

9. Safety Analysis

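### The per-protocol set cannot contain PAH-targeted therapy events from listed drugs taken before PEA, yet the SAP analyses in it the composite that counts those events

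*SAP*

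**What the plan says.** **The exclusion rule.** SAP 4.3.3 restricts the PPS to patients who, among other conditions, "have not taken any prohibited medication". Protocol 7.6 has the same rule: "have not taken any prohibited medication, have no significant protocol deviations". Neither states a period.

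**What is prohibited, and when.** The SAP does not define prohibited medication. The only text that does so is Protocol 5.8: "no drugs named in the exclusion criteria may be administered to patients on riociguat therapy". Exclusion criteria 11 and 12 in Protocol 4.1.2 name the PAH drug classes (ERAs, PDE5 inhibitors, prostanoids) as well as nitrates and NO donors. Riociguat is not on the list. On the end of treatment, Protocol 3.1 says: "The study drug will be discontinued once PEA is performed".

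**Where the PPS is used.** SAP 8.2.2 tabulates and tests the composite in the PEA set and the PPS. For the therapy component it says: "All PAH-targeted therapy from randomisation until 6 months after PEA will be included". SAP 8.3 uses the same two sets for an exploratory endpoint that starts at surgery: "The proportion of patients who need PAH-targeted therapy immediately after PEA to Visit 4 will be summarised using the frequency counts and percentages". SAP 4.3.3 describes the PPS as supportive.

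**The concern.** An analysis set should not be defined by the absence of an event that is then counted in it. Here, use of an ERA, PDE5 inhibitor or prostanoid before PEA is both a component of a secondary endpoint and a ground for leaving the set in which that endpoint is supportively tested. SAP section 11, item 4, deliberately moved the start of the composite from PEA to randomisation. In the PPS, the exclusion rule takes out the listed-drug events that this change brought in.

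The missing window adds a second problem. Concomitant medication is recorded through Visit 4, so those who fix the PPS at the blind data review will see postoperative use and will have no written rule for it. If they applied the criterion to the whole study, patients given a listed class for residual disease after surgery would also go. The PPS analyses of Visit 2 PVR (measured before surgery), Visit 4 PVR and post-PEA PAH therapy would then be selected on a postoperative outcome.

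What is at stake is the supportive role of the PPS. Agreement or disagreement with the PEA set on this endpoint would partly reflect the definition of the set.

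**Working it through.** The plan gives no rate or timing of PAH-targeted therapy, so there is no figure of its own to reproduce. The rates below are assumptions, shown as ranges.

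**Inputs**

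- Patients per arm: 40, from the target of 80 completers in Protocol 4.3.3 and 1:1 allocation.
- p: share of operated patients with any PAH-targeted therapy from randomisation to 6 months after PEA. Assumed 10% to 30%.
- f: share of those users who took a listed class before PEA. Assumed 10%, 25% or 50%.
- q: share of the remaining, post-PEA users who took a listed class and would also be excluded. q = 0 if the ban ends at PEA.
- The other PPS criteria are ignored, and patients are taken to stay on study drug until PEA.

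**Formulas**

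- Share of users removed: r = f + (1 − f)q
- PPS rate for the component: p(1 − r) / (1 − pr)

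For 0 < p < 1, the PPS rate is below p whenever r > 0. The direction is therefore fixed, and only the size depends on the assumptions.

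**Ban ends at PEA (q = 0, so r = f)**

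With p = 20% there are 8 users among 40.

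- f = 10%: 0.8 removed on average; 7.2/39.2 = 18.4%
- f = 25%: 2 removed; 6/38 = 15.8%
- f = 50%: 4 removed; 4/36 = 11.1%

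PPS rate over the range of p:

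| p | f = 10% | f = 25% | f = 50% |
|---|---|---|---|
| 10% | 9.1% | 7.7% | 5.3% |
| 20% | 18.4% | 15.8% | 11.1% |
| 30% | 27.8% | 24.3% | 17.6% |

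**Effect on a difference between arms.** Assume 30% use on placebo and 15% on riociguat, that is 12/40 v 6/40, a 15-point difference.

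- f = 50%: 6 and 3 patients are removed, leaving 6/34 = 17.6% v 3/37 = 8.1%, a difference of 9.5 points.
- f = 10%: 0.27/0.97 = 27.8% v 0.135/0.985 = 13.7%, a difference of 14.1 points.

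**The whole composite.** Every patient removed in this way has a composite event. If C is the composite rate and e = pf the share removed, the PPS rate is (C − e)/(1 − e), which is below C whenever C < 1. The size cannot be given, because the documents state no rates for the composite or for its other components: death, PH-related hospitalisation, and functional class unchanged or worse.

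**Criterion applied to the whole study (p = 20%, f = 10%)**

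- Half of post-PEA users on a listed class (q = 0.5): r = 0.1 + 0.9 × 0.5 = 0.55; PPS rate 0.09/0.89 = 10.1%; 40 × 0.2 × 0.55 = 4.4 excluded per arm.
- All on a listed class (q = 1): r = 1; PPS rate 0%; 8 excluded per arm.

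Under the ban-ends-at-PEA reading with the same p and f, 0.8 patients per arm are excluded.

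**The case against.** The strongest reply is that Protocol 5.8 already supplies the window. It bans the listed drugs for patients on study therapy, study drug stops at PEA, and nothing in either document prohibits PAH-targeted therapy afterwards. Need for such therapy after surgery is itself a planned endpoint. On this reading the SAP 8.3 endpoint lies wholly after the banned period, as do about 6 of the composite's 9 months. Removing patients who took a banned drug while on study drug is also what a per-protocol set is for. The PEA set has no medication criterion and is reported beside the PPS. The PPS is only supportive, all analyses are exploratory, and membership is fixed under blind review.

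Most of this stands, and it limits the point. A reader might infer that the PPS loses most or all PAH-therapy events by definition, so that both arms fall to zero. The documents do not support that. With the ban ending at PEA, losing most events would require more than half of the use to fall before surgery, and nothing in the documents suggests this. Even on the whole-study reading, zero follows only if every user took a listed class. Riociguat is not listed, and the protocol synopsis notes its approval for persistent or recurring CTEPH after surgery. Nor does a listed drug given in the ICU after PEA cost a patient a place in the PPS for Visit 2 PVR, unless the criterion is stretched beyond the period in Protocol 5.8.

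The reply does not remove the overlap before PEA. There, one act is both an event and an exclusion under the stated rules. Blind review settles who is in the set, but it does not make those events countable.

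**Conclusion.** The concern holds in a limited form. With the ban running to PEA, listed-class use between first dose and PEA cannot appear as an event in the PPS composite, and the PPS rate for the therapy component is biased downwards. At an assumed 20% use, the bias runs from 1.6 points (f = 10%) to 8.9 points (f = 50%). These figures rest on assumed rates and timing and on all pre-PEA use being of a listed class.

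Under that reading, the SAP 8.3 endpoint loses only patients who also took a listed drug before PEA. The wider selection on a postoperative outcome arises only if the unwindowed wording is applied to the whole study. That is possible as the SAP stands: it sets a V0 to V2 window for its medication subgroups (SAP 4.4 and 7.1) but none here. The ITT and PEA-set analyses are not affected, so the main results are not in question.

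**What to change.** - **SAP 4.3.3:** limit the criterion to prohibited medication taken from first dose of study drug up to PEA, to match the period in Protocol 5.8. This would also settle the case of a patient who stops study drug early and takes a listed drug before surgery, which Protocol 5.8 leaves open.
- **SAP 8.2.2:** report the composite in the PEA set only. Alternatively, count it in the PPS only from PEA onward, with a note that listed PAH-targeted therapy before PEA is excluded by definition.
- **SAP 8.3:** no change. With the window stated, the post-PEA therapy analysis can stay in the PPS.
- **SAP section 11:** record the change before the blind data review that fixes PPS membership.

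This is SAP wording only. It needs no new data and does not alter which drugs patients may receive. The downside is that one supportive table is dropped or relabelled.

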4.3.4. Safety Set

The safety set will consist of all patients who received any study drug. All analyses using the safety set will group patients according to treatment actually received.

The safety set will be used in safety analyses.

4.4. Subgroups

Safety analyses (see Section 9.1) will be performed for the following subgroups for AEs occurring between V0 and V2:

- Intake of concomitant DOACs or NOACs being reported during V0 to V2
- Intake of concomitant vitamin K antagonists being reported during V0 to V2
- Intake of concomitant β -blockers being reported during V0 to V2

5. Patient Disposition

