4.1.1 Inclusion Criteria

Each patient must meet all of the following criteria to be enrolled in this study:

1. Is a male or nonpregnant and nonlactating female patient aged from 18 to 80 years, both inclusive
2. Is diagnosed with operable CTEPH and anticipating symptomatic and/or prognostic benefit from PEA
3. Has PVR >800 dyn·s·cm⁻⁵
4. Has undergone RHC not more than 180 days before Visit 1
5. Has been treated with anticoagulants for at least 90 days before Visit 1
6. Has ability to swallow oral medication
7. Has ability and willingness to participate and access to the health facility
8. Is capable of understanding the written informed consent and provides signed and witnessed written informed consent
9. Female patient must be either surgically sterile, postmenopausal (no menses for the previous 12 months), or must be practicing an effective method of birth control as determined by the investigator (eg, oral contraceptives, double barrier methods, hormonal injectable or implanted contraceptives, tubal ligation, or male partner with vasectomy or complete abstinence)

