7.1. Prior and Concomitant Medications

All concomitant medications taken by the patient during the study, from the date of signature of the informed consent will be recorded in the appropriate section of the eCRF. This will include all prescription drugs, herbal products, vitamins, minerals, and over-the-counter medications. Any changes in concomitant medications will also be recorded in the patient's eCRF.

A prior medication is defined as any medication that is ended prior to the date of first dose of study drug. A concomitant medication is defined as any medication that has a stop date that is on or after the date of first dose of study drug. Imputation for partial medication start dates and stop dates can be found in Appendix 13.4. Medications with completely missing stop dates will be classified as concomitant.

Medications reported on the Concomitant medications eCRF page will be presented in data listings for prior medications and concomitant medications. Concomitant medications will be summarised by the following subgroups:

- Intake of concomitant DOACs or NOACs being reported during V0 to V2: Yes/No;
- Intake of concomitant vitamin K antagonists being reported during V0 to V2: Yes/No.
- Intake of concomitant β -blockers being reported during V0 to V2: Yes/No

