9.1.1. Incidence of Treatment Emergent Adverse Events

A treatment-emergent adverse event (TEAE) is defined as any event not present before exposure to study drug or any event already present that worsens in either intensity or frequency after exposure to study drug. If start date of an AE is missing after imputation, the corresponding AE will be included as TEAE if end date of AE is after the first dose of study drug or the end date is also missing. Imputation for partial AE start dates and end dates can be found in Appendix 13.4.

The number and percentage of patients with at least one TEAE will be summarised by MedDRA system organ class (SOC) and preferred term (PT). At each level of SOC or PT, a patient will be counted only once if the patient reported multiple events.

The above analysis will also be conducted for TEAEs occurred from V0 to V3 and by subgroups as defined in section 4.4.

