9.1.7. TEAEs of Special Interest

The following TEAEs of special interest will be defined and included in summary tables by treatment group:

MedDRA coding

- “Myocardial infarction” and “Acute myocardial infarction” as preferred term;
- “Haemorrhage” will be assessed by using the standardised MedDRA query (SMQ);
- “Hypotension”, “haemoptysis”, “syncope” will be assessed as preferred term;
- “Stroke” will be assessed by using the preferred terms “haemorrhagic stroke”, “ischaemic stroke” and “embolic stroke”.

The TEAEs of special interest will be summarized by group: Myocardial infarction, Haemorrhage, Hypotension, Haemoptysis, Syncope, Stroke and also by study period V0 to V2, V0 to V4, medication of interest subgroup as defined in Section 4.4. The number of patients along with number of events in each level of summary will be provided.

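### The three safety subgroups are set by drugs taken up to V2, the same window in which adverse events are counted, so a drug started because of an event puts that event in the drug's Yes row

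*SAP*

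**What the plan says.** Protocol 7.7 plans no subgroup analyses and leaves any of special interest to the SAP. SAP 4.4 then names three and opens with the event window: "Safety analyses (see Section 9.1) will be performed for the following subgroups for AEs occurring between V0 and V2". Membership is by "Intake of concomitant DOACs or NOACs being reported during V0 to V2", by "Intake of concomitant vitamin K antagonists being reported during V0 to V2", and by beta-blocker intake over the same period.

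SAP 7.1 adds two details:

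- Each subgroup is its own binary variable, for example "Intake of concomitant vitamin K antagonists being reported during V0 to V2: Yes/No". A patient can be Yes on more than one.
- A concomitant medication is "any medication that has a stop date that is on or after the date of first dose of study drug". This looks only at the stop date. A drug that ended before the first dose is classed as prior, but there is no limit on how late a concomitant drug may have started.

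SAP 9.1 uses these subgroups throughout. Section 9.1.1 says: "The above analysis will also be conducted for TEAEs occurred from V0 to V3 and by subgroups as defined in section 4.4". Sections 9.1.2 to 9.1.6 carry a similar sentence that also mentions the overall Safety set. Section 9.1.7, on events of special interest, asks for results "by study period V0 to V2, V0 to V4, medication of interest subgroup as defined in Section 4.4".

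**The concern.** Subgroup membership is settled by drug use after randomisation, in the period in which the outcome is observed. An event can therefore cause the membership under which it is reported.

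This is plausible in this trial. All patients must be anticoagulated, and the events of special interest include haemorrhage, haemoptysis, stroke and hypotension. A bleed could prompt a change of anticoagulant, and a cardiac event could prompt a beta-blocker to be started.

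The table for the newly started drug would then show a raised event rate that the drug did not produce, and its No row would look too clean. If riociguat alters how often events occur, or if drug changes after events differ by arm, membership itself depends on treatment. Riociguat-placebo comparisons inside a subgroup then lose the protection of randomisation.

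**Working it through.** **Step 1: is there a rule on time order?** SAP 4.4 asks only for intake reported up to V2. SAP 7.1 asks only that the drug was not stopped before first dose. Neither document ties intake to event onset, uses status at first dose, or says how to classify a patient who switches. The window that matters in practice is drugs ongoing at first dose or started between first dose and V2.

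**Step 2: size.** The plan gives no subgroup size, subgroup event rate or switch rate, so there is no figure to reproduce. The only documented input is 88 patients randomised 1:1, or 88/2 = 44 per arm. The rest are assumptions:

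- q = share on a DOAC at first dose, the others on a VKA: 0.5 (range 0.3 to 0.7)
- p = true event rate, equal on both drugs: 15% (range 5% to 25%)
- s = fraction of VKA patients with an event who are then switched to a DOAC before V2: 30% (range 10% to 50%); nobody else switches

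Formulas:

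- DOAC Yes rate = p[q + (1−q)s] / [q + (1−q)ps]
- DOAC No rate = p(1−s) / (1−ps)

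Central case, in expected counts for one arm: 22 patients start on each drug, with 22 × 0.15 = 3.30 events in each group. Switched: 3.30 × 0.30 = 0.99.

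| Row | Events / patients | Rate |
|---|---|---|
| DOAC Yes | (3.30 + 0.99) / (22 + 0.99) = 4.29 / 22.99 | 18.7% |
| DOAC No | (3.30 − 0.99) / (22 − 0.99) = 2.31 / 21.01 | 11.0% |
| VKA Yes | 3.30 / 22 | 15.0% |
| VKA No | 3.30 / 22 | 15.0% |

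The DOAC Yes/No ratio is 1.70, where the truth is 1.00. The VKA rows stay correct because a switched patient remains VKA Yes. The two Yes rows together hold 4.29 + 3.30 = 7.59 events against 6.60 in the arm, so 0.99 of an event is counted twice.

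With q and p as above, the Yes/No ratio is 1.19 at s = 10% (16.3% vs 13.7%) and 2.58 at s = 50% (20.9% vs 8.1%). Over the full ranges:

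- The Yes/No ratio runs from 1.12 to 3.99.
- The DOAC Yes rate divided by the true rate runs from 1.03 (q = 0.7, p = 25%, s = 10%: 0.73/0.7075) to 2.05 (q = 0.3, p = 5%, s = 50%: 0.65/0.3175).

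The same algebra applies to beta-blockers, with q the share on one at first dose and s the share of untreated patients with an event who are started on one.

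**Step 3: comparison between arms.** With the same p and s in both arms, both DOAC Yes rows read 18.7% and the comparison is undisturbed. If p is 15% in both arms but s is 30% in one and 10% in the other, the rows read 18.7% and 16.3%. That is a gap of 2.4 points (ratio 18.7/16.3 = 1.15) with no treatment effect.

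**Step 4: event window.** SAP 4.4 fixes V0 to V2. Sections 9.1.1 to 9.1.6 name V0 to V3 in the same sentence as the subgroups. Section 9.1.7 names V0 to V2 and V0 to V4. Visit 3 is after surgery, so a table to V3 takes in operative events such as the blood loss listed in SAP Appendix 13.3. Events after V2 cannot influence drug status up to V2, but they change what the table describes.

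**Step 5: after the fix.** With membership fixed by the drug in use at first dose, both rows equal p and the ratio is 1.00 in every scenario.

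**The case against.** The strongest reply has four parts.

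- **The tables are modest.** They show counts and percentages, with no test on adverse events, in a trial whose analyses the protocol calls exploratory. This stands, and it limits the weight of the point. It does not make a mislabelled row right.
- **Time order can be checked by hand.** Adverse events are listed with start and end dates, and medication dates and changes are recorded. This also stands, but a reader of the summary table would not know to look.
- **The size is assumed.** This is true: no switch rate is given, and if no event leads to a drug change there is no bias. A reader might infer from a small made-up example that the DOAC rate would be multiplied several times. The documents do not support that. Over the ranges tried, the Yes rate is at most about twice the true rate, and the central case moves about one event per arm.
- **First-dose status misattributes too.** A patient switched early who has an event weeks later on the new drug would be reported under the old one. This is a real cost, and the fix has to deal with it.

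A reader might also take SAP 4.4 and 9.1 to contradict each other outright on the window. The sentence in 9.1.2 to 9.1.6 can be read as V0 to V3 for all patients plus subgroup tables under the window of 4.4. It is an ambiguity, but one a programmer would have to guess at.

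**Conclusion.** The point holds for the descriptive safety subgroup tables and nothing else; no efficacy analysis is touched. As defined, a drug started because of an event places that event in the drug's Yes row, and no other provision corrects this.

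Two stronger readings are not supported:

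- **That the event leaves its proper row.** After a VKA-to-DOAC switch it stays in VKA Yes and appears in DOAC Yes as well, so it is double-counted. What it leaves is DOAC No.
- **That the randomised comparison is lost outright.** It is compromised only if event rates or event-driven drug changes differ between arms, and the documents do not show that they will.

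The size is unknown. Under the stated assumptions (half on a DOAC, 15% event rate, 30% of VKA patients with an event switched) the table would read 18.7% against 11.0% with no true difference. In arms of 44, one reclassified event is enough to be noticed. The correction is cheap and worth making before the SAP is final.

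**What to change.** In SAP 4.4 and 7.1, define each of the three subgroups by whether the drug was in use at the first dose of study drug: started before that date and not stopped before it. List later starts and switches separately, with dates.

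The data should be available. Protocol 5.8 requires drug names and administration dates, and eligibility requires that the patient "Has been treated with anticoagulants for at least 90 days before Visit 1". That criterion does not name a class and says nothing about beta-blockers, so class and beta-blocker status must come from the medication records. SAP Appendix 13.4 sets a start date with a missing day in the month of first dose to the first-dose day, so the rule should say how a start on that day is treated.

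Optionally, add one sensitivity table that classifies each event by the drug in use on its onset date.

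State one event window for the subgroup tables and use it in 4.4 and in 9.1.1 to 9.1.7. If a second period is wanted for events of special interest, say so in 4.4.

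The cost is SAP wording and a small derivation, with no new data. The downside is that drugs started after first dose no longer define a subgroup, so in the main table an event on a later-started drug is attributed to first-dose status. The listing and the onset-based table would show those cases.
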